9.6. Electrocardiograms

12-lead ECGs will be performed in triplicate, approximately 2–5 minutes apart while the subject is resting (See Schedule of Assessments for timing of ECGs ([Appendix 1](#), [Appendix 2](#), and [Appendix 3](#))).

9.7. Laboratory Tests

Laboratory tests listed on the Schedule of Assessments ([Appendix 1](#), [Appendix 2](#), and [Appendix 3](#)) will be analyzed at a local laboratory and used in all safety analyses and or response assessments (see [Appendix 4](#), [Appendix 5](#), and [Appendix 6](#)). PK samples discussed in [Section 9.14](#) will be shipped to a central laboratory for analysis.

The following are descriptions of the tests to be performed. For timing and frequency of the below listed tests, refer to the Schedule of Assessments ([Appendix 1](#), [Appendix 2](#), and [Appendix 3](#)):

- CBC with differential – WBCs, ANC, red blood cells (RBCs), hemoglobin (Hgb), hematocrit (Hct), platelets, mean corpuscular hemoglobin (MCH), and differential
- Serum chemistry – glucose, blood urea nitrogen (BUN), creatinine, sodium, potassium, chloride, calcium, phosphate, uric acid, phosphorus, carbon dioxide, alkaline phosphatase (ALP), aspartate aminotransferase (AST), alanine aminotransferase (ALT), total bilirubin, total protein, albumin, and lactate dehydrogenase (LDH). (Additional chemistry will be performed as indicated in the TLS management plan and as clinically indicated.)
- Coagulation – activated partial thromboplastin time (aPTT), PT, and INR
- Urinalysis (Dipstick)
- Pharmacokinetic sampling – see [Section 9.14](#)

- Pharmacodynamic and biomarker studies – see [Section 9.12](#), Site Laboratory Manual and Schedule of Assessments
- Pregnancy test – serum/urine pregnancy test in females of childbearing potential
- HIV testing
- Hepatitis B core antibody, surface antibody and surface antigen, and hepatitis C virus antibody (HCV Ab) tests are required. Hepatitis B polymerase chain reaction (PCR) is required if hepatitis B core antibody and/or surface antigen is positive. Hepatitis C PCR is required if HCV Ab test is positive.
- Cytogenetics
 - Classical cytogenetics for subjects with AML only. At least 20 bone marrow metaphases are needed to define a normal karyotype and recommended to describe an abnormal karyotype. Abnormal karyotypes may be diagnosed from blood specimens. If abnormal cytogenetics at screening, repeat cytogenetics in a subject with CR/CRi to confirm a cytogenetic remission.
 - Fluorescence in situ hybridization [FISH] for subjects with SLL or CLL only – FISH for del(13q), del(11q), del(17), trisomy 12, del(6q) performed on blood or biopsy specimen. Result is not required prior to enrollment
- IgHV mutational testing (subjects with SLL or CLL only) – IgHV mutational testing performed in the peripheral blood lymphocytes or biopsy specimen. Result is not required prior to enrollment
- Quantitative serum immunoglobulin levels (IgA, IgG, IgM) will be performed for subjects with SLL and CLL
- Screening for gene mutations and gene rearrangements for subjects with AML only. Screening is not required for enrollment in the study but will be collected if performed as part of the standard of care, including genes defined in the 2017 ELN response criteria. If obtained as screening, repeat the test for the genetic marker by RT-qPCR or flow cytometry in a subject with CR/CRi to confirm CR with minimal residual disease per the 2017 ELN response criteria.
- Bone marrow aspiration/biopsy are required for assessment of response and as clinically indicated. For subjects with CLL/SLL, FL, MCL, MZL, DLBCL, and high-grade B-cell lymphomas refer to [Appendix 5, Table 19](#) and [Appendix 6, Table 21](#). For subjects with AML refer to [Appendix 4, Table 18](#). Additionally, for monotherapy cohorts, optional biopsy/aspirates pre-first dose, at the end of Cycle 6 and at end of treatment may be conducted for correlative studies. See Laboratory Manual. For AML combination therapy cohorts, bone marrow aspirate/biopsy and laboratory evaluation should be completed at screening (up to 28 days prior to starting venetoclax), Cycle 2 Day 1, and Day 1 of every subsequent cycle until a CR or CRi is achieved. Thereafter, response assessments should be performed when bone marrow examinations are obtained as clinically indicated and at EOS. Both biopsy and aspirate are recommended for disease assessment, but biopsy may be omitted if aspirate is considered to be sufficient. Bone marrow aspirate sample collected at the time of disease assessment may be used for exploratory biomarker analysis in bone

marrow/bone marrow aspirate. If any remaining sample is available after evaluation for disease assessment, it should be submitted to the central laboratory for pharmacodynamic biomarker/correlative study (refer to the Lab Manual).

- Tumor biopsy – Formalin fixed material is acceptable although fresh tissue is preferred.
- Chest X-ray, unless recent CT scan shows no pulmonary abnormalities (for patients treated with voruciclib/venetoclax combination therapy).

9.8. Disease Assessment

Computed tomography (CT) scans, positron emission tomography (PET)-CT scans, bone marrow aspirate/biopsy, and laboratory evaluation will be completed as appropriate for individual subjects. For subjects with CLL/SLL, efficacy assessments will be based on criteria of the IWCLL guidelines per [Appendix 5](#). For subjects with FL, MCL, MZL, DLBCL, and high grade- B-cell lymphomas, efficacy assessments will be based on the Lugano Classification response criteria per [Appendix 6](#). For subjects with AML, efficacy assessments will be based on European LeukemiaNet (ELN) Response Criteria per [Appendix 4](#).

9.9. ECOG

Eastern Cooperative Oncology Group (ECOG) performance status to be evaluated at Screening, Day 1 of each cycle, and EOS.

9.10. Pregnancy Test

Serum pregnancy test in females of childbearing potential at screening, urine pregnancy test Day 1 of each cycle and at EOS.

9.11. Virology

HIV antibody testing is required to determine eligibility.

Hepatitis B core antibody, surface antibody and surface antigen, and hepatitis C virus antibody (HCV Ab) tests are required to determine eligibility. Hepatitis B polymerase chain reaction (PCR) is required if hepatitis B core antibody and/or surface antigen is positive. Hepatitis C PCR is required if HCV Ab test is positive.

9.12. Compliance Diary

A compliance diary will be provided to the subject at each study drug dispensing timepoint, according to the Schedule of Assessments ([Appendix 1](#), [Appendix 2](#), and [Appendix 3](#)).

9.13. Dispensation, Administration, and Accountability of Voruciclib and Venetoclax

Voruciclib is administered orally once daily on dosing days, on an empty stomach at least 1 hour prior to food, or 2 hours after food at approximately the same time each day. On days of PK sampling, subjects should be instructed not to take voruciclib until after the pre-dose PK sample is collected.

Venetoclax is commercially available as 10 mg, 50 mg, and 100 mg tablets. Venetoclax is to be taken once daily with a meal and water.

In order to minimize intestinal P-gp interaction, venetoclax must be taken with a meal, followed by voruciclib administration 2 hours later.

A compliance diary assessment and returned drug accountability will be performed at each visit which includes voruciclib dispensing. Refer to [Section 5](#) for additional information on the storage and management of voruciclib and venetoclax.

9.14. Pharmacokinetics

Pharmacokinetic (PK) samples are to be obtained as noted below:

9.14.1. Voruciclib Monotherapy

In monotherapy IS Cohorts 1-5:

Pre-dose specimens should be drawn within 2 hours prior to dosing and post-dose within ± 30 minutes of designated post-dose sampling times.

Samples for voruciclib plasma concentration analysis will be collected as follows:

- Cycle 1 Day 1: Pre-dose, 4-, and 6-hours post-dose
- Cycle 1 Day 2: Pre-dose (24 hours after the preceding last dose)
- Cycle 1 Day 8: Pre-dose (24 hours after the preceding last dose)
- Cycle 1 Day 15: Pre-dose (24 hours after the preceding last dose), 4- and 6-hours post-dose

In monotherapy IS Cohorts 6-11:

- Cycle 1 Day 1: Pre-dose, 4-, and 6-hours post-dose
- Cycle 1 Day 2: Pre-dose (24 hours after the preceding last dose)
- Cycle 1 on Day 8 (24 hours after the preceding last dose)
- Cycle 1 Day 15 (24 hours after the preceding last dose, if applicable [Day 15 samples only to be collected for IS2w2w schedule])
- Cycle 2 Day 1: Pre-dose

9.14.2. Voruciclib + Venetoclax Combination Therapy

Pre-dose specimens should be drawn within 2 hours prior to dosing and post-dose within +30 minutes of designated post-dose sampling times.

Blood samples for characterization of **voruciclib PK** will be collected in Cohorts 12–19 and 21–25 as shown in [Table 14](#) and [Table 15](#), relative to dosing of voruciclib.

Table 14: PK Sample Collection for Voruciclib, Cohort 12 (QOD Dosing)

Cycle	Day	Time of Collection	
		Pre-dose	Post-dose
1	3	X	2, 4, 6 hours
	4*	-	approximately 24 hours after Day 3 dose
	8	-	approximately 24 hours after Day 7 dose
	13	X	2, 4, 6 hours
	14	-	approximately 24 hours after Day 13 dose
	21	anytime during clinic visit	
2	1	X	-
4, 6	1, 14 (± 3 days)	anytime during clinic visit	
Every 3 cycles thereafter	1, 14 (± 3 days)	anytime during clinic visit	

* Day 4 sample to be collected only if the subject is able to visit the clinic.

Table 15: PK Sample Collection for Voruciclib, Cohorts 13–19 and 21–25 (QD Dosing)

Cycle	Day	Time of Collection	
		Pre-dose	Post-dose
1	3	X	2, 4, 6 hours
	4*	X (approximately 24 hours after Day 3 dose)	-
	8	X (approximately 24 hours after Day 7 dose)	-
	14	X	2, 4, 6 hours
	15	-	approximately 24 hours after Day 14 dose
	21	anytime during clinic visit	
2	1	X	-
4, 6	1, 14 (± 3 days)	anytime during clinic visit	
Every 3 cycles thereafter	1, 14 (± 3 days)	anytime during clinic visit	

* Day 4 sample to be collected only if the subject is able to visit the clinic.

Drug-Drug Interaction (DDI) Assessment: Voruciclib exposures (when co-administered with venetoclax) will be compared to historical single agent data to assess DDI and the effect of venetoclax on voruciclib PK.

Blood samples for characterization of **venetoclax PK** will be collected in Cohorts 12–19 and 21–25 as shown in [Table 16](#) and [Table 17](#), relative to dosing of venetoclax.

Table 16: PK Sample Collection for Venetoclax, Cohort 12 (QOD Dosing)

Cycle	Day	Time of Collection	
		Pre-dose	Post-dose
1	13	X	2, 4, 6, 8 hours
	14	X (approximately 24 hours after Day 13 dose)	-
	21	anytime during clinic visit	
2	1	X	2, 4, and 6-hours post-dose of venetoclax (voruciclib to be dosed 6 hours after venetoclax administration, after completion of the 6- hour sample collection)
4, 6	1, 14 (± 3 days)	anytime during clinic visit	
Every 3 cycles thereafter	1, 14 (± 3 days)	anytime during clinic visit	

Table 17: PK Sample Collection for Venetoclax, Cohorts 13–19 and 21–25 (QD Dosing)

Cycle	Day	Time of Collection	
		Pre-dose	Post-dose
1	14	X	2, 4, 6 and 8-hours
	15	X (approximately 24 hours after Day 14 dose)	-
	21	anytime during clinic visit	
2	1	X	2, 4 and 6-hours post-dose of venetoclax (voruciclib to be dosed 6 hours after venetoclax administration, after completion of the 6- hour sample collection)
4, 6	1, 14 (± 3 days)	anytime during clinic visit	
Every 3 cycles thereafter	1, 14 (± 3 days)	anytime during clinic visit	

DDI Assessment: Venetoclax exposure (when co-administered with voruciclib) will be compared to historical single agent data to assess DDI and the effect of voruciclib on venetoclax pharmacokinetics. Venetoclax concentrations on Cycle 2 Day 1 and Cycle 1 Day 14 will also be compared assuming limited effect, if any, on voruciclib on Cycle 2 Day 1.

Voruciclib PK and other relevant data from all clinical trials (including late phase clinical trials) will be pooled and analyzed using population PK methods. Additionally, voruciclib exposure-response and exposure-safety assessments will be performed and the results will be presented in a separate report.

PK of voruciclib in subjects receiving co-administered azole antifungals versus those without azole antifungals will be compared.

Detailed instructions on collection of plasma for determination of voruciclib and venetoclax will be provided in the Site Laboratory Manual.

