4.3.2.1. Administration Schedules and Doses of Voruciclib + Venetoclax

Amendment 11 – IS_{2w,2w} Dosing Schedule

For Cycle 1 in combination cohorts 12–19, the dosing will be as follows ([Table 5](#)):

- Venetoclax will be ramped up starting with 100 mg on Day 1, 200 mg on Days 2–21, then 400 mg administered as a single agent on Days 22–28.
- Voruciclib dosing will be administered on Days 3–14 at the appropriate Cohort Dose ([Table 3](#)).

For Cycle 2 and beyond, the dosing will be as follows:

- Venetoclax 200 mg will be administered on Days 1–21, and 400 mg administered as a single agent on Days 22–28.
- Voruciclib at the cohort dose ([Table 3](#)) on Days 1–14.

Venetoclax should be taken with a meal and water. When both venetoclax and voruciclib are to be taken, venetoclax should be taken first with a meal followed by voruciclib at least 2 hours later (e.g., meal completed at 8 a.m. with venetoclax, dose of voruciclib taken after 10:00 a.m.). Voruciclib tablets must not be chewed, crushed, or broken.

Table 5: Administration Schedules of Voruciclib given in Combination with Venetoclax (IS_{2w,2w})

Administration Schedule of Voruciclib IS _{2w,2w} and Venetoclax per 28-day Cycle					
Cycle 1	Day 1	Day 2	Days 3 to 14	Days 15 to 21	Days 22 to 28
Venetoclax	100 mg	200 mg	200 mg	200 mg	400 mg
Voruciclib QD	-	-	Cohort dose	None	None
Voruciclib QOD ^a	-	-	50 mg ^a	None	None
Cycle 2 and beyond	Days 1 to 14		Days 15 to 21		Days 22 to 28
Venetoclax	200 mg		200 mg		400 mg
Voruciclib QD	Cohort dose		None		None
Voruciclib QOD ^a	50 mg ^a		None		None

Abbreviation: QOD = once every other day

^a For cohort 12, the dose of voruciclib will be 50 mg once every other day (QOD) on Days 3, 5, 7, 9, 11, and 13 of Cycle 1, and on Days 1, 3, 5, 7, 9, 11, and 13 of Cycle 2 and beyond.

Amendment 12 – IS_{3w,1w} Dosing Schedule

For Cycle 1 in combination cohorts 21–25, the dosing will be as follows (Table 6):

- Venetoclax dose will be ramped up starting with 100 mg on Day 1, 200 mg on Days 2–21, then 400 mg administered as a single agent on Days 22–28.
- Voruciclib dosing will be administered on Days 3–21 at the appropriate Cohort Dose (Table 4).

For Cycle 2 and beyond, the dosing will be as follows:

- Venetoclax 200 mg will be administered on Days 1–21, and 400 mg administered as a single agent on Days 22–28.
- Voruciclib at the cohort dose (Table 4) will be administered on Days 1–21.

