In Study P1446A-05/19/08 and Study P1446A-05/20/08, voruciclib PK samples were collected for 24 hours post-dose after single and multiple administrations. Sample collection only during the 24-hour dosing interval precluded reliable estimation of terminal phase half-life. However, effective half-life may be calculated based on accumulation ratio (multiple dose $AUC_{(0-24)}$ divided by single dose $AUC_{(0-24)}$) using the following formula:

Accumulation Ratio = $1 / (1 - \exp(-k_{el} \times \tau))$.

Based on accumulation ratio, voruciclib effective half-life was estimated at the 600 mg and 350 mg dose levels in Study P1446A-05/19/08 and Study P1446A-05/20/08, respectively. These dose levels were chosen because of the large sample size of 16 and 24, respectively, thus permitting a robust estimation. Based on average accumulation ratios of 2.06 and 2.77, voruciclib effective half-life value was estimated to be 24 to 36 hours.

Preliminary PK results for voruciclib and venetoclax for Cohorts 12 (voruciclib 50 mg QOD) to 15 (voruciclib 150 mg QD) indicate that administration of multiple doses of voruciclib does not have an effect on venetoclax PK. In these cohorts, on Cycle 1 Day 21 (i.e., 7 days after the last voruciclib dose on Cycle 1 Day 14), plasma voruciclib concentrations were either below the lower limit of quantitation or very low. At the highest voruciclib dose level evaluated for PK (150 mg QD, Cohort 15), average plasma voruciclib concentration on Cycle 1 Day 21 was 8 ng/mL (less than 2% of maximum plasma concentration) indicating nearly complete elimination of voruciclib from the systemic circulation one week after the last dose. Lack of pharmacokinetic interaction at steady-state and very low voruciclib concentrations observed one week after the end of treatment justifies administration of the labeled dose of venetoclax on voruciclib treatment-free days. Therefore, in Cohorts 21–25 (voruciclib $IS_{3w,1w}$) the labeled dose of venetoclax (400 mg QD) may be administered on Days 22 to 28 of each cycle when voruciclib is not administered.

Sequence of administration

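### Cohorts 21–25 share the PK sampling days of the two-weeks-on schedule, so no draw of either drug is scheduled on Days 22–28, when venetoclax goes to 400 mg one day after the last voruciclib dose

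*Protocol*

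**What the plan says.** Protocol Section 9.14.2 sets the sampling in Table 15, "PK Sample Collection for Voruciclib, Cohorts 13–19 and 21–25 (QD Dosing"), and Table 17, "PK Sample Collection for Venetoclax, Cohorts 13–19 and 21–25 (QD Dosing"). Appendix 3 repeats both. The scheduled days are:

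- Voruciclib, Cycle 1: Days 3, 4, 8, 14 (serial), 15 and 21.
- Venetoclax, Cycle 1: Days 14 (serial), 15 and 21.
- Both drugs: Cycle 2 Day 1, Days 1 and 14 of Cycles 4 and 6, then every third cycle.

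The Day 21 sample may be taken at any hour of the visit. The Day 15 voruciclib sample stands in the post-dose column as "approximately 24 hours after Day 14 dose".

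Section 4.3.2.1 gives the two groups different Cycle 1 dosing days. For Cohorts 12–19: "Voruciclib dosing will be administered on Days 3–14 at the appropriate Cohort Dose". For Cohorts 21–25: "Voruciclib dosing will be administered on Days 3–21 at the appropriate Cohort Dose". In both groups venetoclax steps from 200 mg to 400 mg on Day 22.

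Section 4.3.2.2 supports that step with data from Cohorts 12–15 on two grounds. The first is that multiple doses of voruciclib had no effect on venetoclax PK. The second is very low voruciclib "on Cycle 1 Day 21 (i.e., 7 days after the last voruciclib dose on Cycle 1 Day 14"). It concludes that in Cohorts 21–25 "the labeled dose of venetoclax (400 mg QD) may be administered on Days 22 to 28 of each cycle when voruciclib is not administered".

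The SAP adds no sampling. Its Section 5.3 refers back to the protocol, and its Section 8.8 leaves the PK analysis to a separate plan.

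**The concern.** The sampling days fit a schedule whose last Cycle 1 voruciclib dose is on Day 14. There, Day 15 is the first day without a dose and Day 21 is a 7-day washout sample. In Cohorts 21–25 neither is true.

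The washout evidence in Section 4.3.2.2 was taken 7 days after the last dose, yet it is applied to cohorts in which 400 mg begins 1 day after it. The days on which residual voruciclib and 400 mg venetoclax overlap most are the days on which nothing is planned to be measured. They also lie within the 28-day DLT period, so a toxicity then would have no planned concurrent exposure data. The PK of both drugs in combination is a secondary objective (Section 2.2).

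**Working it through.** **1. The two schedules side by side (Sections 4.3.2.1 and 9.14.2)**

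| Cycle 1 | Cohorts 13–19 | Cohorts 21–25 |
|---|---|---|
| Last voruciclib dose | Day 14 | Day 21 |
| First 400 mg venetoclax dose | Day 22 | Day 22 |
| Gap between the two | 22 − 14 = 8 days | 22 − 21 = 1 day |
| Day 15 voruciclib sample | no dose that day | dosing day, so in effect a trough |
| Day 21 sample | 7 days after last dose | last dosing day, hour not fixed |
| Scheduled draws, Days 22–28 | none | none |
| Cycle 2 Day 1 (Day 29) | 15 days after last dose | 8 days after last dose |

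Table 15 itself shows the labelling slip. Its Day 4 and Day 8 samples, also about 24 hours after a dose and with another dose due, stand in the pre-dose column. Table 14 for Cohort 12 puts its 24-hour samples in the post-dose column because no dose is due on those days. The Day 15 entry follows the second pattern, which fits Cohorts 13–19 only.

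**2. The protocol's half-life, reproduced.** Section 4.3.2.2 gives R = 1/(1 − exp(−k·τ)), with τ = 24 h and R = 2.06 and 2.77. The fraction left after one day is f = 1 − 1/R, and t½ = 24·ln 2/(−ln f).

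- R = 2.06: f = 0.515, t½ = 25.0 h.
- R = 2.77: f = 0.639, t½ = 37.1 h.

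The protocol states 24 to 36 h, so each value agrees to about 1 h.

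**3. Residual voruciclib in Cohorts 21–25.** Take the Day 22 level (24 h after the last dose) as 100% and assume mono-exponential decay. The remainder n days later is fⁿ.

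- Day 23: 51% to 64%.
- Day 24: 0.515² to 0.639² = 26% to 41%.
- Day 28: 0.515⁶ to 0.639⁶ = 2% to 7%.

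Section 1 also gives a range of 24 to 48 h. At 48 h, 71% would remain on Day 23.

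**4. Check against observed data.** Day 28 is 7 days after the last dose in these cohorts. Section 4.3.2 gives a monotherapy pre-dose level of 0.9 µM and a Cmax of 1.5 µM, a ratio of 0.6. On that ratio, 7% of trough is about 4% of Cmax and 2% of trough is about 1%. Section 4.3.2.2 observed less than 2% of Cmax at 7 days in Cohort 15. The lower end agrees with this; the upper end looks too high.

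**The case against.** The strongest reply is that Section 4.3.2.2 does not rest on washout alone. If voruciclib at steady state leaves venetoclax PK unchanged, half or two-thirds of a trough matters less. The Day 14 and 15 samples will also test the interaction in every QD combination cohort up to 350 mg, at higher voruciclib levels than occur on Days 22–28. Much of this stands. Its limit is that the data in hand are preliminary and stop at 150 mg QD, while Cohorts 22–25 run from 200 to 350 mg. Section 4.15 still holds venetoclax at 200 mg during co-administration because of a possible interaction.

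A reader might go further in four ways that the documents do not support.

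- **That the window is wholly unobserved.** The Cycle 2 Day 1 pre-dose draw gives a venetoclax trough about 24 h after the Day 28 400 mg dose, and voruciclib 8 days after its last dose. Visit windows (±3 days in Cycle 1; −7/+2 days later) may also put a draw inside Days 22–28, but only by chance.
- **That the 400 mg step is unsupported, or that venetoclax exposure will rise.** The residual percentages concern voruciclib only, and nothing here shows an effect on venetoclax.
- **That the table was copied without thought.** The documents show one shared table; how it arose is inference.
- **That the serial profile should move to Day 21.** Day 14 follows 12 daily doses, and Section 1 puts steady state by 14 days. The Day 14 ECGs and pharmacodynamic samples are also paired with that profile (Section 9.15, Appendix 3).

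The Day 21 sample is not useless either. The planned population PK analysis can use a sparse sample if its time is recorded. Nor is the Day 15 value lost, since its timing relative to the Day 14 dose is fixed.

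**Conclusion.** The shared schedule does not fit Cohorts 21–25. One sample is mislabelled, one has lost its purpose, and no draw of either drug is scheduled on Days 22–28. The 7-day washout observation is applied where the gap is 1 day rather than 8.

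The protocol's accumulation ratios imply that about 51–64% of the Day 22 voruciclib level remains on Day 23 and 26–41% on Day 24. This assumes mono-exponential decay at the effective half-life, and the upper figures are probably high. Cycle 2 Day 1 covers the end of the window but not Days 22–25, when residual voruciclib is highest.

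The consequence is a gap in the secondary PK objective and in the evidence for one leg of the dosing rationale. It does not show that the rationale is wrong. The correction is cheap enough to make.

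**What to change.** Give Cohorts 21–25 their own rows in Tables 15 and 17 and in Appendix 3:

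1. Keep the Day 14 serial profile with its paired ECG and pharmacodynamic samples.
2. Move the Day 15 voruciclib sample to the pre-dose column.
3. Replace the untimed Day 21 sample with one time-recorded sample of both drugs on a fixed day early in Days 22–28, for example Day 23 or 24, before that day's venetoclax dose and after at least one 400 mg dose. Exempt this draw from the ±3-day window; otherwise a Day 23 visit could slip back to Day 20, a dosing day.
4. Reconcile the Section 4.3.2.2 rationale with the 1-day gap in these cohorts. No view is taken on the dose.

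Cost: the sparse Day 21 sample is lost and one visit moves by 2–3 days. The number of draws is unchanged.

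Limit: a Day 23 or 24 venetoclax trough follows only one or two 400 mg doses, against seven by Cycle 2 Day 1. A comparison of the two would mix accumulation with any interaction, and the documents give no venetoclax half-life with which to separate them.
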